## 7 Safety and Adverse Events

### 7.1 Definitions

#### 7.1.1 Adverse Event

An **adverse event** (AE) is any symptom, sign, illness or experience that develops or worsens in severity during the course of the study. Intercurrent illnesses or injuries should be regarded as adverse events.

Abnormal results of diagnostic procedures are considered to be adverse events if the abnormality:

- results in study withdrawal
- is associated with a serious adverse event
- is associated with clinical signs or symptoms
- leads to additional treatment or to further diagnostic tests
- is considered by the investigator to be of clinical significance

For FDA regulated studies the FDA defines an adverse event as the following:

Adverse event means any untoward medical occurrence associated with the use if a drug in humans whether or not considered drug related.

#### 7.1.2 Serious Adverse Event

Adverse events are classified as serious or non-serious. A **serious adverse event** is any AE that is:

- fatal
- life-threatening
- requires or prolongs hospital stay
- results in persistent or significant disability or incapacity
- a congenital anomaly or birth defect
- an important medical event

Important medical events are those that may not be immediately life threatening, but are clearly of major clinical significance. They may jeopardize the subject, and may require intervention to prevent one of the other serious outcomes noted above. For example, drug overdose or abuse, a seizure that did not result in in-patient hospitalization or intensive treatment of bronchospasm in an emergency department would typically be considered serious.

All adverse events that do not meet any of the criteria for serious should be regarded as **non-serious adverse events**.

### 7.2 Recording of Adverse Events

At each contact with the subject, the investigator will seek information on adverse events by specific questioning and, as appropriate, by examination. Information on all adverse events will be recorded immediately in the source document, and also in the appropriate adverse event module of the case report form (CRF). All clearly related signs, symptoms, and abnormal diagnostic procedures results should be recorded in the source document, though should be grouped under one diagnosis.

All adverse events occurring during the study period will be recorded. The clinical course of each event will be followed until resolution, stabilization, or until it has been determined that the study intervention

or participation is not the cause. Serious adverse events that are still ongoing at the end of the study period will be followed up to determine the final outcome. Any serious adverse event that occurs after the study period and is considered to be possibly related to the study intervention or study participation will be recorded and reported immediately.

### ***7.3 Relationship of AE to Study***

The relationship of each adverse event to the study procedures should be characterized. The PI or medical monitor will determine how the relationship of the AE will be classified as:

- likely related – a well-known effect of the device or clearly not related to the subject or environmental factors
- probably related – is known or suspected effect of device or cannot be readily explained by subject or study procedures
- possibly related – is a possible effect of the device or can be explained by the subject or study procedures
- unlikely related – is not a suspected effect of the device or can readily be explained by the subject or environmental factors
- unrelated – is not a known effect of the device and can readily be readily and easily explained by the subject or environmental factors

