#### **7.4.2 Investigator reporting: notifying the study sponsor**

Investigators from all participating sites should report all unexpected and related adverse events, regardless of whether they are serious or not, and all unanticipated problems to the sponsor.

Any study-related unanticipated problem posing risk to subjects or others, and any type of serious adverse event, will be reported to the study sponsor by telephone within 24 hours of the event. To report such events, a Serious Adverse Event (SAE) form will be completed by the investigator and emailed to the study sponsor within 24 hours. The investigator will keep a copy of this SAE form on file at the study site. Report serious adverse events by sending via email to: [Evolus., Company Call Center: [name] ([name]), Company Email: [contact]]

Within the following 48 hours, the investigator will provide further information on the serious adverse event or the unanticipated problem in the form of a written narrative. This should include a copy of the completed Serious Adverse Event form, and any other diagnostic information that will assist the understanding of the event. Significant new information on ongoing serious adverse events should be provided promptly to the study sponsor.

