### 9.1 Risks

All treatments used in this protocol will be used according to the FDA approved intended use. No unexpected risks should occur. Risks that may be experienced from any injection are swelling bruising, redness, itching, infection, or pain.

There is minimal risk to this study. This study is a prospective observational study of an FDA approved cosmetic drugs used as approved. The study protocol only adds 3D imaging required to make the observational measurements. The images will be identifying as they are of the face. All identifying images will be stored on a database or computer behind the firewall and a password.

Potential risks of the neuromodulators are:

- dry mouth
- discomfort or pain at the injection site
- tiredness
- headache
- neck pain
- eye problems: double vision, blurred vision, decreased eyesight, drooping eyelids, swelling of your eyelids, and dry eyes.
- drooping eyebrows
- allergic reactions. Symptoms of an allergic reaction may include: itching, rash, red itchy welts, wheezing, asthma symptoms, or dizziness or feeling faint.
- upper respiratory tract infection

Reproductive risks: If patient is of child-bearing potential, a urine pregnancy test may be administered prior to injection to confirm negative pregnancy status. The effects of this drug/device, there could be serious harm to unborn children or children who are breast-feeding. These effects could also harm the mother.

CONFIDENTIAL

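### The adverse-event causality scale in 7.3 is written for a device in a drug trial, and its five classes overlap, so one event can be probably, possibly and unlikely related at once

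*Combined protocol and SAP*

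**What the plan says.** Section 7.3 opens by asking for the relationship of each event to the study procedures, then gives five classes:

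- The highest class, *likely*, is worded: "a well-known effect of the device or clearly not related to the subject or environmental factors"
- The second, *probably*, also offers two alternative tests: "is known or suspected effect of device or cannot be readily explained by subject or study procedures"
- The third, *possibly*, has the same two-part form: "is a possible effect of the device or can be explained by the subject or study procedures"
- The fourth, *unlikely*, again needs only one of its tests: "is not a suspected effect of the device or can readily be explained by the subject or environmental factors"
- The last, *unrelated*, is the only class that requires both of its tests: "is not a known effect of the device and can readily be readily and easily explained by the subject or environmental factors"

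The interventions (3.1, 5.2.1) are four injected neuromodulators, which 9.1 calls drugs. The only equipment described as a study measure is the 3D camera (3.3). Section 9.1 lists potential risks of the neuromodulators, including headache, tiredness and "upper respiratory tract infection".

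A causality judgement is used in three rules:

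- Follow-up (7.2) may end once neither the intervention nor taking part is judged to have caused the event; the rule begins "The clinical course of each event will be followed until resolution, stabilization, or until it has been determined that the study intervention".
- Serious events arising after the study period (7.2) are recorded and reported if thought possibly related.
- Sponsor reporting (7.4.2): "Investigators from all participating sites should report all unexpected and related adverse events, regardless of whether they are serious or not".

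Section 7.4 also requires the initial narrative report to give the investigator's view of the association with the study intervention. No section states which of the five classes count as related.

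**The concern.** A causality scale should place each event in one class, so that two assessors with the same facts reach the same answer. Here every class asks about the wrong object, and in four of them meeting either of two quite different tests is enough. The same facts can then be entered as related or as unlikely to be related, both in accordance with the protocol. Explanation by the subject counts toward *possibly* and also toward *unlikely*. Study procedures, which include the injection, appear in *probably* and *possibly* as a rival explanation alongside the subject, although they are part of what the subject is exposed to. Where a rule in 7.2 or 7.4.2 turns on causality, its outcome would depend on which test the assessor happened to apply.

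**Working it through.** The plan gives no figure on this point, so there is none to reproduce. The check is logical. Its inputs are the five definitions in 7.3, the risk list in 9.1, and the rules in 7.2, 7.4.1 and 7.4.2.

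**1. Read the device as the toxin, and test a listed risk.** Take an event that 9.1 lists and that the subject or environment readily explains, for example headache in a subject with migraine. Assume that a listed risk is at least a known effect.

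| Class | First test | Second test | Joined by | Met? |
|---|---|---|---|---|
| likely | well-known effect: open, since 9.1 says only potential risk | clearly not due to subject or environment: fails | or | only if regarded as well known |
| probably | known or suspected: met | no ready explanation in subject or procedures: fails if the subject explains it | or | yes |
| possibly | possible effect: met | explained by subject or procedures: met if the subject explains it | or | yes |
| unlikely | not suspected: fails | readily explained: met | or | yes |
| unrelated | not known: fails | readily and easily explained: may be met | and | no |

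Three classes are met on the text, and a fourth if the effect is regarded as well known. If the effect is suspected but not yet known, and is readily and easily explained, *unrelated* is met as well as *probably*, *possibly* and *unlikely*.

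**2. Test an unlisted event**, since a listed risk would rarely be called unexpected under 7.4.2. An event either has or lacks a ready explanation in the subject or study procedures. If it lacks one, it meets the second test of *probably*. If it has one, it meets the second test of *possibly*. If it is also not a suspected effect, it meets the first test of *unlikely*. So an unlisted, unsuspected event also meets classes on both sides.

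**3. Count the overlaps.** Code the definitions as written on a 5 by 5 grid. One axis is effect of the product: not possible, possible, suspected, known, well known. The other is alternative explanation: clearly not related, unclear, explainable, readily, readily and easily. Subject, environment and procedures are treated as one explanation axis.

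- Exactly one class: 0 combinations. Two classes: 7. Three: 14. Four: 4. Check: 7 + 14 + 4 = 25.
- *Likely* and *unlikely* together: 4 of 25. *Likely* and *unrelated* together: 0 of 25.
- At least one of *likely*, *probably*, *possibly* together with at least one of *unlikely*, *unrelated*: 5 + 5 + 2 + 2 + 2 = 16 of 25, going from not possible to well known.

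These counts depend on the assumed grid. The overlap in steps 1 and 2 does not.

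**4. Replace every 'or' with 'and'.** The *likely*/*unlikely* overlap disappears. However, 12 combinations then fit one class, 5 fit none and 8 fit more than one (7 fit two and 1 fits three). Check: 12 + 5 + 8 = 25.

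**5. Test an event plainly caused by the injection.** It fails the second test of *probably* and meets the second test of *possibly*. It also meets the second test of *likely*, because it is clearly not due to the subject or environment. The scale again gives several answers, but does not force a lower one.

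**6. Set the class against each safety rule.**

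| Rule | Depends on causality? |
|---|---|
| Recording of in-study events (7.2) | no, all are recorded |
| In-study serious events to sponsor within 24 hours (7.4.2) | no, any type |
| Unanticipated problems to sponsor (7.4.2) | no, all are reported |
| Follow-up of serious events (7.4.1) | no, all are followed until they resolve or stabilise |
| End of follow-up, non-serious events (7.2) | yes |
| Serious events after the study period (7.2) | yes |
| Unexpected, non-serious events to sponsor (7.4.2) | yes, if related |

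**The case against.** The strongest reply is that this is leftover template wording with little practical effect. Section 7.1.1 speaks of drug-related events, 7.2 and 7.4 of the study intervention, and 9.1 uses drug/device for the injected product, so an investigator would read the device as the toxin. Neither 7.2 nor 7.4.2 cites the scale in 7.3, and 7.2 states its own causality test. The labels suggest a dividing line between *possibly* and *unlikely*, and 7.2 uses *possibly related* as its threshold for post-study serious events.

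Much of this stands. A reader might infer that a drooping eyelid would be graded *unlikely* because the camera did not cause it. That reading is strained, since 9.1 lists drooping eyelids as a neuromodulator risk. The link from 7.3 to the rules is an inference, though a natural one, because 7.3 holds the protocol's only causality classes.

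The reply does not remove the overlap, which was derived with the device already read as the toxin. Nor does a dividing line between *possibly* and *unlikely* help when the same event meets classes on both sides of it.

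**Conclusion.** The point holds as a drafting defect in an operative safety rule. Section 7.3 names the wrong object and its classes are not exclusive. A listed risk with a ready alternative explanation meets three classes at once, or four if it is regarded as well known. The consequence is limited to the three causality-dependent decisions in the last table. It should be corrected, but it does not threaten the strain endpoint.

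Several stronger conclusions are tempting and not supported:

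- *Serious events could go unreported during the study.* In-study serious events and unanticipated problems go to the sponsor whatever the class.
- *A respiratory infection definitely spans likely to unlikely.* The *likely* end needs the effect to be well known, and 9.1 lists it only as a potential risk.
- *Events caused by the injection are downgraded.* They also meet *likely* by its second test.
- *A planned comparison of related events between products is undermined.* Sections 3.4 and 6 plan none. Any such summary, if later made, would rest on an ambiguous class.

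The verdict rests on reading the definitions literally, on treating a listed risk as at least a known effect, and on 7.3 supplying the judgement used in 7.2 and 7.4.2.

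**What to change.** In 7.3, including its opening sentence, name the study drug or injection procedure as the exposure in place of the device. Replace the five definitions with a pair that is exclusive and exhaustive: *related*, meaning a reasonable possibility that the study drug or injection procedure caused the event, and *not related*, meaning no such possibility. State in 7.2 and 7.4.2 that this is the classification they use.

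If five levels are kept, rewrite them so that every event fits exactly one, treat study procedures as part of the exposure, and state that *possibly*, *probably* and *likely* count as related.

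The cost is protocol wording and one case report form field, with no added visits or staff. The small downside of the two-level scale is less gradation.

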### ***7.4 Reporting of Adverse Events, Adverse Device Effects and Unanticipated Problems***

Investigators and the protocol sponsor (which may or may not be a Penn Investigator) must conform to the adverse event reporting timelines, formats and requirements of the various entities to which they are responsible,

If the report is supplied as a narrative, the minimum necessary information to be provided at the time of the initial report includes:

• Study identifier

• Study Center

• Subject number

• A description of the event

• Date of onset

	

• Current status

• Whether study intervention was discontinued

• The reason why the event is classified as serious

• Investigator assessment of the association between the event and study intervention

---	--

Additionally, all other events (unanticipated problems, adverse reactions, unanticipated adverse device effects and subject complaints will be recorded and reported with respect to institutional and federal policies.

#### ***7.4.1 Follow-up report***

If an SAE has not resolved at the time of the initial report and new information arises that changes the investigator's assessment of the event, a follow-up report including all relevant new or reassessed information (e.g., concomitant medication, medical history) should be submitted to the IRB. The investigator is responsible for ensuring that all SAE are followed until either resolved or stable.

#### **7.4.2 Investigator reporting: notifying the study sponsor**

Investigators from all participating sites should report all unexpected and related adverse events, regardless of whether they are serious or not, and all unanticipated problems to the sponsor.

Any study-related unanticipated problem posing risk to subjects or others, and any type of serious adverse event, will be reported to the study sponsor by telephone within 24 hours of the event. To report such events, a Serious Adverse Event (SAE) form will be completed by the investigator and emailed to the study sponsor within 24 hours. The investigator will keep a copy of this SAE form on file at the study site. Report serious adverse events by sending via email to: [Evolus., Company Call Center: [name] ([name]), Company Email: [contact]]

Within the following 48 hours, the investigator will provide further information on the serious adverse event or the unanticipated problem in the form of a written narrative. This should include a copy of the completed Serious Adverse Event form, and any other diagnostic information that will assist the understanding of the event. Significant new information on ongoing serious adverse events should be provided promptly to the study sponsor.

#### **7.4.3 Investigator reporting: notifying the Penn IRB**

For single and multi-site studies each site PI will need to follow their local IRB reporting requirements in addition to the protocol outlined reporting.

#### **7.4.4 Sponsor reporting: Notifying Participating Investigators**

For clinical trials, in addition to reporting certain unanticipated problems and adverse events noted above to the FDA, it is the responsibility of the study sponsor to report those same adverse events or findings to participating investigators.

### **7.5 Medical Monitoring**

It is the responsibility of the site Principal Investigator to oversee the safety of the study at his/her site. This safety monitoring will include careful assessment and appropriate reporting of adverse events as noted above. The lead PI will monitor all AEs reported.

### **7.6 Confidentiality**

Information about study subjects will be kept confidential and managed according to the requirements of the Health Insurance Portability and Accountability Act of 1996 (HIPAA). Those regulations require a signed subject authorization informing the subject of the following:

- What protected health information (PHI) will be collected from subjects in this study
- Who will have access to that information and why
- Who will use or disclose that information
- The rights of a research subject to revoke their authorization for use of their PHI.

In the event that a subject revokes authorization to collect or use PHI, the investigator, by regulation, retains the ability to use all information collected prior to the revocation of subject authorization. For subjects that have revoked authorization to collect or use PHI, attempts should be made to obtain permission to collect at least vital status (i.e. that the subject is alive) at the end of their scheduled study period.

CONFIDENTIAL

### ***7.7 Data Collection and Management***

REDCap will be used to store and maintain the primary study records. The data entered into REDCap will be obtained from the study-relevant patient EMRs. Study personnel will be granted access to this project created in REDCap with each user obtaining individual access authenticated by a login system. Minimal patient identifiers will be collected and stored in the REDCap database. Patient name and date of birth will be collected in REDCap.

Source data will mainly be from the patient's EMR. When the study requires data not normally collected in the patient's EMR, the case report forms will also be the source document. Data from source documents (Appendix 15.4, case report forms (case report forms definition- Appendix 15.5), will be entered into an electronic data capturing system. All source documents should be secure in private spaces with restricted access. After Visit 1 the FACE-Q will be sent electronically to the subject for each follow-up visit via a REDCap survey.

During procurement of data charts will be reviewed in private spaces to ensure the confidentiality of acquired data. Data will be stored for up to 7 years after completion of the last follow-up visit of the last patient randomized. Data may be collected for up to two years following the treatment.

### ***7.8 Records Retention***

The Principal Investigator at each site is responsible for storing regulatory documents, subject files and financial records for the period specified by law. The time period for maintaining research records is defined first by HIPAA regulations that require any HIPAA-regulated information, authorizations, waivers, etc. must be maintained for at least 6 years subsequent to the Institutional Review Board (IRB) acknowledgement of the termination of the research project and secondly by DHHS regulations (45 CFR 46.115) and FDA regulations (21 CFR 56.115) state that IRB records relating to research shall be retained for at least 3 years after completion of the research.

## **8 Study Monitoring, Auditing, and Inspecting**

### ***8.1 Study Monitoring Plan***

This study will be closely monitored by the PI and the project manager. The PI will be participating and the data will be collected by the PI and one other study team member from the patient's EMR. The study team member will enter the data into the REDCap and the project manager will monitor the entry to verify the compliance with respect to the protocol, data collection and source documents.

### ***8.2 Auditing and Inspecting***

The investigator will permit study-related monitoring, audits, and inspections by the EC/IRB, the sponsor, government regulatory bodies, and University compliance and quality assurance groups of all study related documents (e.g. source documents, regulatory documents, data collection instruments, study data etc.). The investigator will ensure the capability for inspections of applicable study-related facilities (e.g. pharmacy, diagnostic laboratory, etc.).

Participation as an investigator in this study implies acceptance of potential inspection by government regulatory authorities and applicable University compliance and quality assurance offices.

CONFIDENTIAL

